1. REPORTING & ANALYSIS PLAN SYNOPSIS

Overview	Key Elements of the RAP
Purpose	
 The purpose of this Reporting and Analysis Plan is to describe all planned analyses and outputs required for the Clinical Study Report (CSR) of study 204987. This amendment covers changes to the study following the interim analysis review of 11 participants.
Protocol	
 This RAP amendment is based on the protocol (Dated 23/SEP/2016, GSK Document No.: 2016N283626_00) and protocol amendments 1 & 2 & 3 (Dated:24/FEB/2017, GSK Document No. : 2016N283626_01 & 07/MAR/2017, GSK Document No. : 2016N283626_02 & 06/MAR/2018 GSK Document No. : 2016N283626_03) of study GSK2586881/204987
Study Design	
 The study will be a single centre, randomised, placebo-controlled and double blind (sponsor open). Subjects will be randomised to receive a single IV dose of GSK2586881 or saline in a crossover design. Approximately 25 subjects will be enrolled to ensure that a minimum of 20 subjects complete all dosing and critical assessments (the target of 20 may be revised by the sample size re-estimation)
Primary Objective	
 To evaluate the effect of a single IV dose of GSK2586881 on the HPV response in healthy volunteers during exercise under hypoxic conditions
Primary Endpoint	
 Change from baseline of Pulmonary Artery Systolic Pressure (PASP) measured via Echocardiography
Planned Analyses	
 An Interim Analysis was planned after approximately 10 patients had completed periods 1 and 2 of the study, to aid the team in decision making with regards to stopping the study for futility or a re-assessment of sample size. Following the interim (referred to as study Part 1), amendments were made to the study before re-starting Part 2. Further interim reviews are planned when approximately 3 and 6 participants have completed periods 1 and 2 in Part 2 of the study. All decisions regarding final analysis, as defined in this RAP document, will be made prior to Database Freeze.
Analysis Populations	
 All Subjects Screened Population will contain all subjects that complete at least one Visit 1 (Screening) procedure. The Modified Intent-to-Treat (mITT) Population will comprise all randomised subjects, excluding those who were randomised in error. The Modified Intent-to-Treat (mITT1) Part 1 Population will comprise all subjects in the mITT Population, who were randomised into Part 1 of the study. The Modified Intent-to-Treat (mITT2) Part 2 Population will comprise all subjects in the mITT Population, who were randomised into Part 2 of the study The Pharmacokinetic (PK) Population will comprise all subjects in the mITT Population, for whom a PK sample was obtained and analysed and on active treatment.

Overview	Key Elements of the RAP
	
 The Pharmacokinetic (PK1) Population Part 1 will comprise all subjects in the mITT Population, randomised in Part 1 of the study, for whom a PK sample was obtained and analysed and on active treatment. The Pharmacokinetic (PK2) Population Part 2 will comprise all subjects in the mITT Population, randomised in Part 2 of the study, for whom a PK sample was obtained and analysed and on active treatment.
Hypothesis	
 No formal statistical hypotheses are being tested. A Bayesian statistical analysis framework with non-informative priors for model parameters (unless otherwise specified) will be used to obtain posterior distributions for effects of interest. These posterior distributions will be used to obtain a number of probability statements about the magnitude of treatment effects (e.g. probability of any treatment related reduction in PASP, or probability that the treatment related reduction in PASP ≥ 5 mmHg). A rule of thumb for “end of study success” is if the probability of any treatment related reduction in PASP (T3-T0) exceeds 0.95 (success is also conditional on the probability of (absolute) treatment related reductions in oxygen saturation exceeding 5% being small).
Primary Analyses	
 The primary endpoint, change from baseline in PASP following exercise under hypoxic conditions (Ti-T0) will be analysed using a Bayesian repeated measures mixed effects regression model, to compare the effects of Placebo vs GSK2586881. Analyses will be performed for Part 1 and Part 2 separately.
Secondary Analyses	
 Pharmacodynamic/Biomarker: RAS peptide responses: Ang II, Ang(1-7), Ang(1-5) will be analysed in a manner similar to the primary endpoint using Bayesian repeated measures mixed modelling to compare the effects of Placebo vs GSK2586881, for Part 2, if data permit. Part 1 data may also be analysed. Data from Part 1 and Part 2 will also be presented descriptively. Safety: Oxygen saturation will be analysed in a manner similar to the primary efficacy endpoint using Bayesian repeated measures mixed modelling to compare the effects of Placebo vs GSK2586881. Analyses will be performed for Part 1 and Part 2 separately. Vital signs, 12-Lead ECG, AEs and Labs will be tabulated and/or listed by treatment group, study part (Part 1 and 2) and timepoint as appropriate. Immunogenicity: Data will be tabulated and/or listed. Pharmacokinetic: Plasma concentrations of GSK2586881 and derived PK parameters will be summarised descriptively/graphically and listed for Part 1 and Part 2 of the study.
Exploratory Analyses	
 Pharmacodynamic/Biomarker: The disease biomarker Surfactant Protein D will be analysed in a manner similar to the primary efficacy endpoint using Bayesian repeated measures mixed modelling to

Overview	Key Elements of the RAP
	
compare the effects of Placebo vs GSK2586881, for Part 2, if data permit. Part 1 data may also be analysed. Data from Part 1 and Part 2 will also be presented descriptively.
 
Ventilatory parameters (Oxygen consumption (VO₂), Carbon dioxide production (CO₂), Total Tidal Volume, Inspiratory Tidal Volume, Expiratory Tidal Volume, Total Respiratory Time, Inspiratory Time, Expiratory Time, Duty Cycle, Mean Respiratory Flow and Respiratory rate) will be summarised descriptively and listed, by treatment group, timepoint and study part (Part 1 and 2).
 
Pulmonary vascular resistance (PVR) will be summarised descriptively and listed, by treatment and timepoint, for Part 2. A statistical analysis similar to that described for PASP will also be performed.
 
• Pharmacogenetics 
Analysis of pharmacogenetic data will be carried out separately by the GSK Genetics team and a separate RAP will be produced. As this is an exploratory endpoint, the results will be available separately to the CSR (or to be included as an appendix).

2. SUMMARY OF KEY PROTOCOL INFORMATION

2.1. Changes to the Protocol Defined Statistical Analysis Plan

There were no major changes or deviations to the originally planned statistical analysis specified in the protocol (Dated: 23/SEP/2016) and protocol amendments 1, 2 and 3 (dated 24/FEB/2017, 07/MAR/2017 and 06MARCH2018).

This amendment details changes to the display of outputs in relation to separate summaries of Part 1 and 2 data (as detailed in protocol amendment 3).

2.2. Study Objective(s) and Endpoint(s)

Objectives	Endpoints
Primary Objective	Primary Endpoint

 To evaluate the effect of a single IV dose of GSK2586881 on the HPV response in healthy volunteers during exercise under hypoxic conditions 	
 Change from baseline of Pulmonary Artery Systolic Pressure (PASP) measured via Echocardiography
Secondary Objectives	Secondary Endpoints

 To evaluate the effect of a single IV dose GSK2586881 on RAS peptide responses To evaluate the safety of a single IV dose of GSK2586881 in healthy volunteers To evaluate the pharmacokinetics of a single IV dose of GSK2586881 	
 Effect of GSK2586881 on baseline levels and changes in response to hypoxia and exercise of RAS peptides (e.g. Ang II, Ang(1-7), Ang(1-5)) Vital signs (heart rate, systolic and diastolic blood pressure) Oxygen saturation 12-lead ECGs Adverse Events (AEs) Immunogenicity Clinical laboratory assessments Continuous pulse oximetry (assessed by the site) Plasma concentrations of GSK2586881 Derived pharmacokinetic parameters
Exploratory Objectives	Exploratory Endpoints

 To evaluate the effect of a single IV dose of GSK2586881 on ventilatory parameters in healthy volunteers during exercise in hypoxic conditions To evaluate the pharmacodynamic activity of a single IV dose of GSK2586881 in healthy volunteers during exercise in hypoxic conditions To evaluate the effect of a single IV dose of GSK2586881 on the HPV response in healthy volunteers under hypoxic 	
Change from baseline of:
 
 Oxygen consumption (VO₂) Carbon dioxide production (CO₂) And other parameters as data permit 
 Change from baseline in Surfactant Protein D and/or additional analytes to be determined Estimation of pulmonary vascular resistance (PVR) measured via Echocardiography

Objectives	Endpoints
conditions (and during exercise under hypoxic conditions).	

 To evaluate Pharmacogenetics 	
 Evaluate I/D polymorphisms in the Angiotensin Converting Enzyme (ACE) gene and analyse the impact on Ang II (and possibly other RAS peptides), hypoxic pulmonary vasoconstriction and responses to GSK2586881 administration

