
will be fitted. Non-informative priors will be used for the model parameters, (see Section 10.8).
 
 Examination of covariates (for example Age, Weight, Height) may take place, if data permit. In this case, the equivalent model may be fitted in PROC MIXED and the covariate assessed at a 10% alpha level. The final Bayesian model would then be fit based upon the final model (after covariate examination) obtained using PROC MIXED. Alternatively, changes in deviance information criteria (DIC) may be assessed as part of the PROC MCMC modelling to examine covariates. Appropriate combinations of the model parameters would be used to obtain posterior distributions for the GSK2586881 vs placebo comparisons at each of the post dosing timepoints (T1 to T4). The change from baseline across the different post-dose timepoints will be represented via adjusted posterior medians for GSK2586881 and placebo, as well as associated 95% equi-tailed credible intervals. These results will be presented within tabular and graphical form after data has been back transformed (if applicable). The difference between GSK2586881 and placebo, for the change from baseline across post-dose timepoints will be represented via adjusted medians, as well as their associated 95% equi-tailed credible intervals. These results will be presented within tabular form after data has been back transformed (if applicable). The posterior distributions will also be used to produce several posterior probability statements, presented in tabular format; the most important being the probability that the change from baseline in PASP is reduced by GSK2586881 at time T3. Posterior probabilities of interest include (looking for high probabilities to favour increases to a lesser extent in PASP on GSK2586881): 
 Probability that change from baseline in PASP is reduced by GSK2586881 (i.e., probability that a treatment difference is negative, or if a log transformation is applied then the probability that the ratio is less than 1). Probability that change from baseline in PASP is reduced by $\geq 2.5\text{mmHg}$ and $\geq 5\text{mmHg}$ by GSK2586881 (i.e., probability that a treatment difference is $\leq -2.5\text{ mmHg}$ and $\leq -5\text{mmHg}$. In the case of a log-transformation, ratios of interest would be <0.95 and <0.90, representing 5% and 10% difference between groups) Probability cut-offs may be re-assessed at the time of analysis

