8.3.2. Planned Pharmacodynamic and Biomarker Statistical Analyses

Planned Statistical Analyses
Endpoint(s)

 • RAS Peptide Responses: Ang II, Ang(1-7), Ang(1-5) • Disease Biomarker: Surfactant Protein D
Model Specification

 • Refer to Section 7.2. Change from baseline in PD/Biomarker endpoints will be analysed in a manner similar to the primary endpoint PASP. Data will be assessed prior to analysis to confirm the need for any data transformations. Log transformation highly likely to be required. • Analyses will be performed for Part 2. Part 1 may also be analysed. • Repeated measures timepoints of interest will be: 
 • Pre-dose (T0) • End of Infusion • 15 min Post-dose (T1) • 15-45 min Post-dose • 60 min post chamber entry (T2) • Immediately post exercise (T3) • Immediately post chamber exit • 30 mins post chamber exit (T4) 
 • Posterior probabilities of interest may include: • AngII: probability that the ratio <1, <0.50 and <0.25, representing any, 50% and 75% greater reduction in AngII levels on GSK2586881 compared to placebo • Ang(1-5) & Ang(1-7): probability that the ratio >1, >1.50 and >1.75, representing any, 50% and 75% greater increase in Ang(1-5) and Ang(1-7) levels on GSK2586881 compared to placebo • SPD: probability that the ratio <1, >1 and >1.5, representing any decrease, any increase and a 50% increase in SPD levels on GSK2586881 compared to placebo • Probability cut-offs may be re-assessed at the time of analysis
Model Checking

 • Refer to Appendix 8: Model Checking and Diagnostics for Statistical Analyses
Model Results Presentation

 • Summary tables for absolute by treatment and timepoint (as detailed above) (for Part 1 and

Planned Statistical Analyses

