
Part 2)
 
 • Listing of absolute data • Individual subject profiles by treatment group and timepoint (for Part 1 and 2) • Summary table of statistical analysis, adjusted change from baseline posterior medians and 95% credible intervals by treatment and timepoint, together with estimated posterior median treatment differences (GSK2586881 – Placebo) and 95% credible intervals for the change from baseline at ALL timepoints (not just T1 to T4), along with posterior probabilities of interest. (Part 2 and Part 1(as required)) • Figure of absolute data by timepoint (for Part 1 and 2) • Figure of statistical analysis adjusted change from baseline medians and 95% credible intervals by treatment group and timepoint (Part 2 and Part 1(as required))

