Echocardiogram	X		X		X		X ⁶ below		X		
Subject enters chamber					X						Subject enters chamber approximately 30 min after study treatment
Study Treatment (Dosing)		X									
Subject leaves chamber							X				Subject leaves chamber after the fourth echocardiogram, blood samples and vital signs have been taken.
Exercise challenge						X					Part 1: exercise at 70% VO ₂ max for ~5-10 min. Echo conducted immediately after. Part 2: exercise at 50% VO ₂ max for 2 min. Echo started at 2 min into the challenge, and the subject continues exercising.
Ventilatory parameters	X		X		X				X		Measurements to be taken 2 min before echocardiograms.

Procedure	Treatment Period 1 and 2 (Washout 3-14 days)										Notes
	Times relative to start of dosing				Hypoxic Challenge ~80 min (Times relative to entry to Chamber)						
	Pre-dose	0h	15 min	15-45 min	0-60 min	60 min	60-70 min	Immediately after exercise	On exit from chamber	After 30 min rest	
Pulse Oximetry (O2 saturation)	←-----→										Will be continuously monitored for safety. A measurement should be recorded at time of each echocardiogram and databased. Part 2: when the echo is recorded during the exercise challenge, pulse oximetry will be recorded immediately prior to initiation of the echo at 2 minutes into exercise.
Telemetry	←-----→										Will be continuously monitored for safety.
RAS Biomarkers	X	X ¹	X ²	X ³		X ²		X ²	X ⁴	X ²	
SP-D	X	X ¹	X ²	X ³		X ²		X ²	X ⁴	X ²	
PK sampling	X	X ¹	X ²	X ³		X ²		X ²	X ⁴	X ²	
AE/SAE review		←-----→									
Concomitant medication review	X										

1. Take at the end of the infusion
2. Taken immediately after echocardiogram
3. Immediately before entering the chamber
4. To be taken as soon as possible after leaving chamber
5. On this occasion ONLY, vital signs to be taken after the blood draw.
6. In Part 2, echo at this time-point taken 2 minutes into the exercise challenge (not immediately after exercise).

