10.3.2. Baseline Definition & Derivations

10.3.2.1. Baseline Definitions

For all endpoints (expect as noted in baseline definitions) the baseline value will be the latest pre-dose assessment. Baseline definitions are applicable to each period.

Parameter	Study Assessments Considered As Baseline		Baseline Used in Data Display
	Screening	Day 1 (Pre-Dose) Time T0	
Safety			
PASP	X	X	T0
Oxygen Saturation		X	T0
Labs	X		Screening
ECGs	X ¹	X	T0
Vital Signs	X ¹	X	T0
Biomarkers/Pharmacodynamic			
RAS peptides		X	T0
Other biomarkers		X	T0
Ventilatory parameters		X	T0

¹Unless otherwise stated, the mean of replicate assessments at any given time point will be used as the value for that time point.

For statistical analyses (for example, Bayesian mixed model for PASP):

- Baseline is defined as the measurement taken pre-dose during each treatment period (i.e., time T0). This can also be referred to as '**period-specific baseline**'.
- Subject-level baseline** is defined as the mean of the two period-specific baseline readings (the pre-dose T0 reading from each of the two treatment periods) for each subject.

- Period-level baseline (or 'adjusted period-specific baseline') is defined as the difference between the baseline ('period-specific baseline') and 'subject-level baseline' for each period and each subject (i.e., the 'period-specific baseline' minus 'subject-level baseline' in each period).

The statistical modelling will include terms for 'subject-level baseline' and 'adjusted period-specific baseline'.

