10.3.2.2. Derivations and Handling of Missing Baseline Data

Definition	Reporting Details
Change from Baseline	= Post-Dose Visit Value – Baseline [Ti – T0]

NOTES :

- Unless otherwise specified, the baseline definitions specified in Section 10.3.2.1 Baseline Definitions will be used for derivations for endpoints / parameters and indicated on summaries and listings.
- Unless otherwise stated, if baseline data is missing no derivation will be performed and will be set to missing.
- The baseline definition will be footnoted on all change from baseline displays.

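### The RAS peptide endpoint includes the drug's effect on the hypoxia and exercise response, but the planned contrasts give only total effects from pre-dose T0, with no interval or probability for the response component

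*SAP*

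**What the plan says.** The secondary endpoint in Section 2.2 is "Effect of GSK2586881 on baseline levels and changes in response to hypoxia and exercise of RAS peptides". It has two components: an effect on levels and an effect on a response.

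Section 8.3.2 sets the analysis: "Change from baseline in PD/Biomarker endpoints will be analysed in a manner similar to the primary endpoint PASP". Under Section 10.3.2.1, "Baseline is defined as the measurement taken pre-dose during each treatment period (i.e., time T0"), and Section 10.3.2.2 defines change as "Post-Dose Visit Value – Baseline [Ti – T0"]. The model in Section 7.2 yields "posterior distributions for the GSK2586881 vs placebo comparisons at each of the post dosing timepoints (T1 to T4"), and Section 8.3.2 extends the reporting for the peptides to "95% credible intervals for the change from baseline at ALL timepoints (not just T1 to T4), along with posterior probabilities of interest".

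The listed probabilities for Ang II are that the ratio is below 1, 0.50 and 0.25, and they are worded as effects on Ang II levels. Tables 5.3 (Part 2) and 5.9 (Part 1, still to be confirmed) follow this structure. No contrast between two post-dose timepoints appears.

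The schedule in Section 10.1.1.2 includes a RAS sample in the 15-45 min slot. Footnote 3 times it as "Immediately before entering the chamber", roughly 30 minutes after dosing. That sample is post-dose and normoxic, but the plan uses it only as one more timepoint referred to T0.

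**The concern.** The infusion falls between T0 and every later sample. A drug that lowers Ang II by the same factor in normoxia and in hypoxia, with no influence on the hypoxic response, would still show a large T0-referenced ratio and near-certain probabilities at T2 and T3. Those are the only inferences planned at the timepoints under hypoxia and exercise, so they are what a report would have to offer for the response component.

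The consequence is for interpretation of a named secondary endpoint. The study is exploratory and has no formal hypotheses, so no error rate is affected.

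**Working it through.** The SAP gives no sample size, variability or expected effect for the peptides, so there is no figure of its own to reproduce. The decomposition is exact; the sizes rest on assumptions.

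**Decomposition.** Let y be the log peptide concentration, D and P the two treatments, and *pre* the pre-chamber sample. Section 8.3.2 expects a log transformation.

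- Planned T3 contrast = [y(T3) − y(T0)]D − [y(T3) − y(T0)]P = A + B
- A = [y(pre) − y(T0)]D − [y(pre) − y(T0)]P, the drug effect present before hypoxia
- B = [y(T3) − y(pre)]D − [y(T3) − y(pre)]P, the difference in change from chamber entry to T3

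On the ratio scale, planned ratio = exp(A) × exp(B). The same holds at T2. The plan reports A and A + B, each with an interval, but not B.

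**Single case (assumed).** The drug cuts Ang II to 25% of placebo from end of infusion onward, and hypoxia acts equally in both arms. The planned T3 ratio is 0.25 × 1.00 = 0.25. With the posterior centred on the true value and a posterior SD s of the log ratio, P(ratio<0.50) = Φ((ln 0.50 − ln 0.25)/s) = Φ(0.693/s):

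- s = 0.2: Φ(3.47) = 0.9997
- s = 0.3: Φ(2.31) = 0.99
- s = 0.4: Φ(1.73) = 0.96

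The response ratio exp(B) is 1.00, with P(ratio<1) about 0.5.

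**Simulation (assumed).** 4000 runs per setting; 10 or 14 complete crossover pairs (Section 3.1.2 plans up to 14 randomised in Part 2); independent errors with SD 0.3, 0.5 or 0.8 per log sample; a 1.3-fold hypoxia/exercise response in both arms, so the true response ratio is 1.00. A flat-prior t posterior on paired differences stands in for the mixed model. The 0.95 mark is only a yardstick; the SAP sets none for the peptides. For 14 pairs and SD 0.5:

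| Normoxic ratio | Planned T3 ratio | Planned: runs with P(ratio<1)>0.95 | Pre-chamber-referenced ratio | Pre-chamber: runs with P(ratio<1)>0.95 |
|---|---|---|---|---|
| 1.00 | 1.00 | 5.1% | 1.00 | 5.2% |
| 0.80 | 0.80 | 20.3% | 1.00 | 4.9% |
| 0.50 | 0.50 | 78.7% | 1.00 | 5.1% |
| 0.25 | 0.25 | 99.9% | 1.00 | 5.1% |

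At a normoxic ratio of 0.50, over both sizes and all three SDs, the planned contrast passes 0.95 in 36% to 99% of runs and the pre-chamber contrast in 4.6% to 5.3%.

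**Why the published summaries are not enough.** SD(B) = √(s₃² + s_pre² − 2ρ·s₃·s_pre), where s₃ and s_pre are the posterior SDs of the T3 and pre-chamber treatment effects and ρ is their posterior correlation, which the tables do not show. With both SDs at an assumed 0.3, SD(B) is 0.42, 0.30 or 0.13 for ρ = 0, 0.5 or 0.9. The median of B can be approximated from the tables, but not its interval or probability.

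**The case against.** A reader might infer that the SAP counts the normoxic drug effect as an effect on the hypoxic response, or that the endpoint is answered with the wrong quantity. The document supports neither. Section 8.3.2 describes its probabilities as effects on peptide levels, which is accurate for a total effect. Reading the first endpoint component as post-dose resting levels is also an interpretation: Section 10.3.2.1 uses baseline for pre-dose T0, and the protocol is not at hand.

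The planned output would also expose the feared case. Ratios are reported at end of infusion, T1 and pre-chamber as well as T2 and T3, and the model figure is to mark the chamber period where possible. A ratio of 0.25 at all of these would visibly not be specific to hypoxia.

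The strongest objection is that the pre-chamber contrast does not isolate the response either. T2 comes 60 minutes after chamber entry and T3 later still, and there is no post-dose session without hypoxia. If the direct ratio drifted from an assumed 0.25 at chamber entry to 0.40 at T3 with the response unchanged, the new contrast would show 0.40/0.25 = 1.60. The value of 1.00 above depends on a constant direct effect.

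Finally, the stakes are modest. The success rule of thumb uses PASP and oxygen saturation only, peptide modelling is conditional on the data, and the wording on probabilities leaves room for more.

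All of this stands and limits the claim. What remains is that one named component of the endpoint has no planned interval or probability, although the data and model can supply one.

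**Conclusion.** The point holds as a gap in the planned inference. The T2 and T3 contrasts are total effects: the drug effect present at chamber entry multiplied by any effect on the hypoxia/exercise response. This follows from the definitions alone. Its size cannot be fixed from the SAP; for an assumed normoxic ratio of 0.50 and no effect on the response, the planned T3 ratio is 0.50 and the response ratio is 1.00.

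It would go too far to conclude that the endpoint should be read from pre-chamber contrasts alone. They remove the drug effect already present at chamber entry but not later drift, so the two sets of contrasts need to be read together. A matching PASP contrast of T3 against T1 is optional and not part of this point.

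**What to change.** In Section 8.3.2 and Tables 5.3 and 5.9:

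- Keep all T0-referenced ratios, and label those at T2 and T3 as the total effect.
- Name end of infusion, T1 and pre-chamber as the timepoints that describe the effect on resting levels.
- Add, from the same posterior draws, the GSK2586881/placebo ratios for T2/pre-chamber and T3/pre-chamber, and T3/T2 for exercise. Give each a 95% credible interval and P(ratio<1) for Ang II, or P(ratio>1) for Ang(1-5) and Ang(1-7). Present them as supportive estimates of the effect on the hypoxia/exercise response.
- State that, without a post-dose normoxic control session, any change in the drug's direct effect between chamber entry and T2 or T3 remains in these ratios, and that the endpoint is interpreted from both sets.

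The cost is some SAP wording and a few derived parameters in the existing MCMC program; the treatment-by-timepoint terms are already in the model and no new data are needed. The new intervals will usually be wider than the T0-referenced ones. With equal posterior SDs s at the two timepoints, the SD of the difference is s√(2(1 − ρ)), which exceeds s whenever ρ is below 0.5.
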